the patient death form CRF. If a patient has been reported as dead at 6 or 12 months on the follow-up CRF (variable *deathyn*) it will be checked against the date of death on the Patient Death CRF (variable *deathdat*). If there is conflicting information between the follow-up form and the death form, the death form will overrule the Follow up CRF. If neither the follow-up form nor the death form have been completed then the TM will check with the site if the patient has died.

3) New long-term residential care at 1 month and 6 months

Subsequent admission to residential care is measured at 1 month, and 6 months follow up (variable *admitryn*). This will be coded as a binary variable (0 = No, 1 = Yes). The 6 months admission to residential care data will include the data collected at the 1 month time point.

4) Cognitive impairment at baseline and 6 months (MoCA)

The Montreal Cognitive Assessment (MoCA) [2] is used to derive a variable for cognitive impairment, and is assessed at baseline and 6 months follow-up. The MoCA comprises 8 sections with a total of 30 questions administered by a qualified health professional (variables *mocavis mocanam mocaatt mocalan mocaabs mocarec mocaori*). A total MoCA score will be derived by summing the score from each section of the questionnaire, only patients with complete MoCA will have a total MoCA score computed, an extra point is added to the total score if the patient has 12 or less years of education. The possible range of scores for the MoCA range from 0 to 30, with a score of 26 or above is considered normal. If the patient is visually impaired or if they are frail and unable to write and draw, the visuospatial/executive section (variable *mocavis*) and the naming section (variable *mocanam*) are excluded and is scored out of 22 instead, a score of 18 or above is considered normal. Cognitive impairment will be coded as a binary variable (0 = score less than 26 (less than 18 if visually impaired), 1 = score 26 or more (18 or more if visually impaired)).

5) Activities of daily living at baseline and 6 months (Barthel index)

The Barthel index [3] is used to derive a variable for activities of daily living, and is assessed at baseline and 6 months follow-up. The Barthel index consists of 10 questions (variables *biadl1 – biadl10*), and has a possible range of scores from 0 (completely dependent) to 20 (completely independent). The final Barthel index score is derived by summing the 10 items.

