Mortality is measured at 3 days, 5 days, 1 month, 6 months, and 12 month follow-up (*deathyn*) and is a binary variable (0 = dead, 1 = alive). The mortality outcome will be summarised at each time point but will only be analysed at 6 and 12 months. The mortality at 12 months outcome will be analysed separately from the 6 months analysis and will not be reported in the main report, instead it will be reported in a separate statistical analysis report. Mortality at 6 months will be reported in the main statistical analysis report. A generalised linear mixed model will be fitted to the data similar to the primary analysis (see section 4.1) with mortality as the dependent variable. The model will include intervention arm, stratification factors (gender and known cognitive decline (IQCODE)) as fixed effects; and centre as a random effect. The adjusted relative risk and 95% CI and p-value for mortality at each time point will be estimated from the model. Mortality at 12 months will be analysed similar to the 6 months mortality data.

4) New long-term residential care at 1 month and 6 months

New long-term residential care is measured at 1 month and 6 months follow-up (*admitryn*) is a binary variable (0 = No, 1 = Yes). A generalised linear mixed model will be fitted to the data with new long-term residential care at 1 and 6 months as the dependent variable. The model will include intervention arm, gender, and known cognitive decline (IQCODE) as fixed effects, and centre as a random effect. The model will include a random intercept for each patient. The model will include an interaction between time and randomised group as a fixed effect. The adjusted relative risk with 95% CI and p-values for new long-term residential care at 1 month and 6 months will be estimated from the model.

5) Cognitive impairment at 6 months (MoCA)

Cognitive impairment measured at baseline and 6 months by the Montreal Cognitive Assessment (MoCA). This is converted into a binary variable (see section 2.1.2). A generalised linear mixed model will be fitted to the data with cognitive impairment at 6 months as the dependent variable. The model will include intervention arm, baseline MoCA score, gender, and known cognitive decline (IQCODE) as fixed effects; and centre as a random effect. The adjusted relative risk with 95% confidence intervals and p-value for cognitive impairment at 6 months will be estimated from the model.

6) Activities of daily living at 6 months (Barthel index)

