Appendix III. Questionnaire scoring

Questionnaire	Possible range of scores	Higher or lower score indicates better health
Charlson Index (Comorbidity)	0-36	Lower
Barthel Index (Activities of daily living)	0-20	Higher
MOCA (Cognitive impairment)	0-30	Higher ≥26 is considered normal (≥18 is considered normal if visually impaired)
IQCODE short (background cognitive status)	1-5 (mean score across all questions)	Lower (3 indicates not much change in last 10 years)
EQ5D VAS (Health status)	0-100	Higher

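### The cognitive impairment model adjusts for a raw baseline MoCA score that is out of 30 for some patients and out of 22 for others, which costs some precision but causes no bias

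*SAP*

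**What the plan says.** SAP section 2.1.2 item 4 derives the total as a plain sum: "A total MoCA score will be derived by summing the score from each section of the questionnaire". On the full form, "The possible range of scores for the MoCA range from 0 to 30, with a score of 26 or above is considered normal". A second rule follows for some patients: "If the patient is visually impaired or if they are frail and unable to write and draw", the visuospatial/executive and naming sections "are excluded and is scored out of 22 instead, a score of 18 or above is considered normal".

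The two cut-offs are then used to make the binary variable: "0 = score less than 26 (less than 18 if visually impaired), 1 = score 26 or more (18 or more if visually impaired". Appendix III gives one range, 0 to 30, and adds that "≥18 is considered normal if visually impaired". It gives no conversion between the forms.

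For the model, section 5.1 item 5 says: "The model will include intervention arm, baseline MoCA score, gender, and known cognitive decline (IQCODE) as fixed effects". It mentions no rescaling and no term for the form used.

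**The concern.** The plan accepts that the two totals are not interchangeable, since it gives each its own cut-off for the outcome. In the same model it then treats them as one measurement on the covariate side. A patient with full marks on the short form (22 of 22) and a patient four points below normal on the full form (22 of 30) enter with the same baseline value, although their chances of being classed as normal at 6 months differ greatly.

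Baseline cognition is likely to be the strongest predictor in this model, and adjusting for it is how the model gains precision. A mixed scale wastes part of that gain. The short form may not be rare: section 2 describes the population as older people with frailty and a level of disability, and frailty with inability to write and draw is one of the two reasons for using it.

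**Working it through.** **1. The plan's own figure.** The SAP gives no number for the MoCA model. Its only sample size, 1050 in section 2.3, sets the scale of the simulation. Inputs: 50% against 40%, 2:1, two-sided 0.05 (sidedness is not stated), 83% power, 6% attrition. The pooled proportion is (0.5 + 2 × 0.4)/3 = 0.433.

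- Controls without continuity correction: [1.96√(1.5 × 0.433 × 0.567) + 0.954√(0.25 + 0.24/2)]² / 0.1² ≈ 313.3, so 314.
- With continuity correction: (313.3/4) × [1 + √(1 + 6/(313.3 × 2 × 0.1))]² ≈ 328.1, so 329.
- Total 3 × 329 = 987, and 987/0.94 = 1050.

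The figure reproduces and this point does not affect it. Fewer than 987 patients will have a 6-month MoCA, because some will have died. The ratios of standard errors below do not depend on the number analysed.

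**2. The two scales.** These come from section 2.1.2 item 4 and need no assumption.

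- Normal on the full form: 26 to 30.
- Normal on the short form: 18 to 22, or up to 23 if the education point is added.
- The ranges do not overlap, because 23 is below 26.
- Prorated by 30/22, short-form scores 18, 19, 20, 21 and 22 become 24.5, 25.9, 27.3, 28.6 and 30.0.
- Cut-offs as a share of the maximum: 18/22 = 0.82 and 26/30 = 0.87.

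**3. Precision.** The SAP gives no short-form share, MoCA mean, SD or correlation, so all of these are assumed. Baseline and 6-month ability were drawn as correlated normals and rounded to a score out of 30, or to 22/30 of it for short-form patients. The outcome was normal or not by the form-specific cut-off. The model was a log-link Poisson regression with robust standard errors, 2:1 allocation, no treatment effect, and no centre, gender or IQCODE terms. Each scenario used 200,000 patients, with standard errors scaled to 987.

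Standard error of the log relative risk for the normal state, at mean 22, SD 5, correlation 0.8:

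| Short-form share | Use of short form | Unadjusted | Raw score | Prorated | Raw + form indicator | Raw ÷ prorated | Raw ÷ indicator |
|---|---|---|---|---|---|---|---|
| 10% | likelier at low cognition | 0.1156 | 0.0934 | 0.0911 | 0.0908 | 1.026 | 1.029 |
| 30% | likelier at low cognition | 0.1108 | 0.0956 | 0.0880 | 0.0873 | 1.086 | 1.095 |
| 50% | likelier at low cognition | 0.1049 | 0.0940 | 0.0836 | 0.0828 | 1.124 | 1.135 |
| 10% | unrelated to cognition | 0.1163 | 0.0958 | 0.0915 | 0.0910 | 1.047 | 1.053 |
| 30% | unrelated to cognition | 0.1092 | 0.0971 | 0.0862 | 0.0851 | 1.127 | 1.141 |
| 50% | unrelated to cognition | 0.1041 | 0.0959 | 0.0823 | 0.0811 | 1.165 | 1.182 |

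Across 24 scenarios (mean/SD 18/6 or 22/5, correlation 0.6 or 0.8, share 10%, 30% or 50%, both patterns of use), raw against prorated inflated the standard error by 0.8% to 16.5%. In all 24 the raw score did better than no adjustment, and raw score plus indicator was at least as precise as prorating.

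**4. Both states of the outcome.** Section 2.1.2 codes the normal state as 1, while section 5.1 speaks of the relative risk of impairment. The precision of a relative risk depends on which state is modelled, so both were run at mean 20-22, SD 5-5.5, correlation 0.85 and share 10-30%. The inflation was roughly 1-6% for the impaired state and 1-16% for the normal state.

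**The case against.** The strongest reply is that the loss is small and rests on assumptions. The SAP does not say how many patients use the short form. If short-form use goes with low cognition, a low raw score is partly correct information and the penalty shrinks, as the upper half of the table shows. This stands, and it limits how much weight the point can bear.

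Two other readings of the text would remove the mixed scale.

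- The covariate could be the baseline binary variable, since section 5.1 item 5 says of MoCA at baseline and 6 months: "This is converted into a binary variable (see section 2.1.2"). But the model sentence says score, and section 2.1.2 defines the score as a sum.
- Section 2.1.2 computes a total only for patients with a complete MoCA, which could leave short-form patients without one. But the provision for scoring them out of 22 points the other way. If this reading were right, they would drop out of the model for lack of a covariate, which is a worse problem.

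A reader might go further and infer three things that the document does not support.

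- *That normal short-form patients are classed as impaired.* The covariate has no threshold, and the classification has its own cut-off of 18 for the short form. Their covariate values only fall in a range that would mean impaired on the full form.
- *That the treatment effect is biased.* The covariate is measured before randomisation, so no bias is expected.
- *That the loss equals the fall in variance explained.* In a simulation with mean 20 and SD 5.5, the share of variance in 6-month MoCA explained by baseline fell from 0.72 to 0.66, 0.62 and 0.58 at short-form shares of 10%, 20% and 30%. The model is for a binary outcome. In a separate run of the same setting, with a similar fall in variance explained, the standard error of the log relative risk rose by 1.0%, 1.7% and 2.1% (impaired) or 2.8%, 6.2% and 8.7% (normal).

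**Conclusion.** The point holds as a small, inexpensive improvement. Followed literally, section 5.1 item 5 puts two scales on one slope and gives away some precision in one secondary outcome. The primary analysis, the sample size and the validity of the comparison between arms are untouched.

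The scale mismatch follows from the SAP's own scoring rules. Its size does not: the ranges given in the last step of the working depend on the assumed MoCA distribution, correlation and short-form share, and on simplified models without centre, gender or IQCODE. At a low short-form share the loss is close to negligible.

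**What to change.** In section 5.1 item 5, state that the model includes the baseline MoCA score together with an indicator for the baseline form used (22-point or 30-point). The indicator should be set for either reason for using the short form. The coding rule in section 2.1.2 and Appendix III name only visual impairment, whereas the scoring rule also covers frail patients unable to write and draw.

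The cost is one extra model parameter. No new data are needed, because the form used must already be known to score the baseline MoCA.

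Entering the score as a proportion of the form's maximum is a second option, but it has a drawback. The two cut-offs do not coincide on that scale, and normal short-form scores of 18 and 19 would still sit below the full-form cut-off (24.5 and 25.9 against 26). It also treats the dropped sections as being as hard as those kept, and it could exceed 1 if the education point is added (23/22). The indicator avoids most of this.

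If the baseline binary variable was intended as the covariate, one sentence saying so would settle the matter instead.

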2.2 TARGET POPULATION

Inclusion Criteria

- Participant is willing and able to give informed consent for the participation in the study.
- If the participant lacks capacity to consent they have a relative or friend who is a 'personal consultee' or Independent Mental Capacity Advocate who will be invited to advise on whether they believe that participation in the study would be in accordance with the values and interests of the individual.
- Male or Female, aged ≥ 65 years.
- Patient had been referred to the admission avoidance HAH service with CGA and would otherwise require hospital admission for an acute medical event. This will include patients presenting with delirium, functional decline, dependence, falls, immobility or a background of dementia presenting with physical disease.
- In the Investigator's opinion, is able and willing to comply with all trial requirements.
- Willing to allow his or her General Practitioner and consultant, if appropriate, to be notified of participation in the trial.
- English speaking.

The presence of a carer will not be a requirement for enrolment and will depend on the individual circumstances of the patient; this will be at the discretion of the clinician responsible for the patient, as is current clinical practice in each centre.

Exclusion Criteria

- Patients with acute coronary syndrome, this includes myocardial infarction and unstable angina and is characterised by cardiac chest pain and is associated with ECG changes.
- Patients presenting with symptoms which require an acute surgical assessment.
- Patients with a suspected stroke.
- Patients who are receiving end of life care as part of a palliative care pathway.
- Patients who refuse HAH service.
- Patients considered by the clinical staff to be too high risk for home based care, for example those who are physiologically unstable, who are at risk to themselves or if the carer reports HAH care who not be acceptable (in keeping with existing clinical practices for HAH).
- Patients living in a residential setting.

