2.4 RANDOMISATION AND BLINDING IN THE ANALYSIS STAGE

Following informed consent and the collection of baseline data eligible patients will be randomly allocated using a 2:1 ratio (2 admission avoidance HAH with CGA: 1 inpatient CGA) by the local member of the research team who recruited the participant. Randomisation will be performed using Sortition, Oxford University's Primary Care Clinical Trail Unit's in-house online randomisation system. Randomisation will be stratified by centre (Bradford, Newport Lanarkshire, Lothian, Fife, Royal Devon Exeter, Torfaen, North Deon, Southern Trust, Guys & St. Thomas, and Belfast), gender and by known cognitive decline.

We have opted for a 2:1 ratio as the HAH schemes have been established to ease the pressure on acute hospital beds and concern was expressed by the clinical leads that a 1:1 randomisation ratio would place unmanageable pressure on the inpatient service. This was therefore a decision related to the capacity of the service to manage patients in the two settings. This has been taken into account in our analysis plan and will not affect the estimated precision of our findings.

Due to the nature of the intervention, it is not possible to blind participants. It will also not be possible to blind research nurses who will collect outcome data as participants will know which intervention they will have received (admission avoidance HAH with CGA or inpatient admission) and are likely to discuss this with the nurse.

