4.2 HANDLING MISSING DATA

The frequency (with percentage) of losses to follow-up (defaulters and withdrawals) over the 6 months of the study will be reported by randomised group and compared between the groups.

The availability of the outcome data for the primary outcome will be summarised by randomised group. The generalised linear mixed model implicitly accounts for data missing at random, however the data missing mechanism will be explored. A logistic regression model will explore any association between baseline characteristics and availability of the primary outcome.

Any changes to the assumptions made in the primary analysis i.e. data missing at random, will be considered in a sensitivity analysis.

The impact of any missing primary outcome data on the primary analysis will be assessed by carrying out a sensitivity analyses based on imputing (multiple imputation) the missing values.

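### The 6-month cognitive impairment model adjusts for a baseline MoCA total that some acutely ill patients will not have, and the SAP gives no rule for keeping them in the analysis

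*SAP*

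**What the plan says.** - **The model.** SAP section 5.1 item 5 takes cognitive impairment at 6 months, a binary variable derived from MoCA, as the outcome. "The model will include intervention arm, baseline MoCA score, gender, and known cognitive decline (IQCODE) as fixed effects"; centre is a random effect.
- **When a baseline score exists.** Section 2.1.2 item 4: "only patients with complete MoCA will have a total MoCA score computed". One relief follows. "If the patient is visually impaired or if they are frail and unable to write and draw", two sections are left out and the test is scored out of 22.
- **Who is tested, and when.** Section 2.2 enrols patients who "would otherwise require hospital admission for an acute medical event", and adds: "This will include patients presenting with delirium, functional decline, dependence, falls, immobility or a background of dementia presenting with physical disease". Patients who lack capacity may enter on the advice of a consultee. Section 2.4 puts baseline before allocation: "Following informed consent and the collection of baseline data eligible patients will be randomly allocated using a 2:1 ratio".
- **Missing data.** Section 4.2 says: "The generalised linear mixed model implicitly accounts for data missing at random, however the data missing mechanism will be explored". The rest of that section deals with loss to follow-up and missing primary outcomes. Section 6 confines sensitivity analyses, including multiple imputation, to the primary outcome unless stated otherwise, and nothing is stated for MoCA.
- **Analysis population.** Section 3.3 aims to retain data wherever it can, so that the analysis is fully intention-to-treat.

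**The concern.** A baseline covariate is in the model to sharpen the estimate. Here it can remove observed outcomes. A patient who was too confused, drowsy or unwell to finish the MoCA at entry, and who then recovered and completed it at 6 months, has an outcome but no covariate value. Standard model fitting drops such a record without comment.

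This can be foreseen from the eligibility criteria, because the baseline test falls in the acute episode. At stake are the precision of a listed secondary outcome and the population to which its result applies. Patients who arrive acutely confused are part of the trial's stated target group, and a result that leaves some of them out describes that group less well.

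**Working it through.** **1. The plan's own figure.** The SAP gives no sample size, power or completion rate for MoCA. Its only figure, 1050, belongs to the primary outcome (section 2.3). It reproduces as follows, for 50% vs 40%, 2:1 allocation (r = 2), difference d = 0.10, 83% power and alpha 0.05 (two-sided assumed):

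- uncorrected control group: n = 314
- continuity-corrected: n' = (n/4)·[1 + sqrt(1 + 2(r+1)/(r·n·d))]² = (314/4)·[1 + sqrt(1 + 6/62.8)]² ≈ 329
- total 329 + 658 = 987, and 987/0.94 = 1050

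The figure is sound, but it neither supports nor refutes this point. Only the 987 is used below.

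**2. Following the rules through for one patient.**

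| Step | SAP rule | Result |
|---|---|---|
| Baseline MoCA unfinished, 22-point version not applicable | 2.1.2 item 4 | no baseline total |
| 6-month MoCA complete | 2.1.2 item 4 | outcome observed |
| Model needs the baseline score | 5.1 item 5 | covariate missing, record omitted by default |
| Rescue by the missing-data plan | 4.2 and 6 | none, primary outcome only |

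Reading the covariate as the binary form of MoCA does not help, because that is derived from the same total. Nor does the missing-at-random statement in 4.2: likelihood methods can accommodate a missing outcome under that assumption, but they do not retain a record whose covariate is absent.

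**3. Comparison with the other instruments.** In section 2.1.2, IQCODE is averaged over whatever items are available, and CAM is derived unless every item is missing. MoCA is the one with an explicit complete-only rule. Barthel has no stated rule for missing items.

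**4. Size, on assumed values.** Let m be the share, among patients with a 6-month MoCA, who lack a baseline total. The number analysed falls by the factor 1 − m, and the standard error rises by about 1/sqrt(1 − m). For counts, assume that 65% of the 987 are alive with a complete 6-month MoCA: 987 × 0.65 ≈ 642.

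| m (assumed) | Omitted of 642 | 1/sqrt(1 − m) | Rise in SE |
|---|---|---|---|
| 5% | 32 | 1.026 | 3% |
| 10% | 64 | 1.054 | 5% |
| 20% | 128 | 1.118 | 12% |
| 30% | 192 | 1.195 | 20% |
| 40% | 257 | 1.291 | 29% |

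If 50% or 80% had a 6-month MoCA (494 or 790 patients), m = 20% would omit 99 or 158. The rise in SE depends on m alone.

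**5. Two scales in one covariate.** A raw 18 is normal on the 22-point version and impaired on the 30-point test. Entered as a raw score, the covariate treats both patients alike. As proportions of the maximum they are 18/22 = 0.82 and 18/30 = 0.60. The two cut-offs then lie at 18/22 = 0.82 and 26/30 = 0.87, close but not identical.

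**The case against.** **The SAP does not say that anyone is discarded.** True. Omission is what happens when the model is fitted as written and nothing more is said. Section 3.3 points the other way but supplies no method.

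**The 22-point version rescues some patients.** It does, and in a frail population this may matter. It does not reach a patient who can see and write but is too confused or unwell to finish.

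**A failed section may simply score zero.** The SAP does not define a complete test, so a delirious patient might have a low total and not a missing one. This stands, and is one reason why the size is unknown.

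**Stronger readings that do not hold.**
- A reader might infer that the comparison between arms is biased or that randomisation is broken. The documents do not support this. Baseline data precede allocation, so selection on a missing baseline MoCA is selection on a pre-randomisation variable and does not by itself bias the contrast.
- A reader might infer that the omitted patients are the most impaired. That is plausible, but the SAP gives no reasons for incomplete tests.
- A reader might take a baseline incompletion rate as the share of 6-month results lost. The denominators differ. Patients who cannot finish at baseline may also be likelier to die or to miss the 6-month test, so m may be smaller than the share of all randomised patients without a total.
- A reader might turn the loss into a fall in power. The SAP does not power this outcome, so any starting power would be invented.

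**Conclusion.** The point holds as a gap with a predictable effect. Two stated rules, the complete-only total and the baseline adjustment, together omit patients with observed 6-month outcomes, and no other section of the SAP repairs this. The consequences are a less precise estimate, a narrower analysed population and a departure from the aim in section 3.3. Bias between the arms is not among them.

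The size cannot be derived from the document. It rests on m, which is assumed: about 5% on the standard error at m = 10% and 12% at m = 20%. The formula also treats omitted patients as carrying average information, which would not be so if nearly all of them were impaired at 6 months. The point concerns one secondary outcome, and it deserves correction because the remedy is standard and cheap.

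**What to change.** Add to SAP section 5.1 item 5:

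- every patient with a 6-month MoCA outcome is analysed;
- where the baseline total is missing, the mean pooled over both arms is entered, together with a missing-baseline indicator (acceptable because the covariate precedes randomisation);
- 22-point and 30-point baseline scores are put on a common scale, for example the proportion of the maximum;
- the number of patients affected is reported by arm.

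Apply the same rule to a missing baseline Barthel in item 6. Baseline CAM in item 2 will rarely need it, because section 2.1.2 already scores partial CAM data.

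**Cost.** A few sentences, the derived variables and one extra model term, with no new data. There is one real downside: if nearly all patients in the indicator group are impaired at 6 months, the relative-risk model may not converge. The SAP should therefore name the fallback in advance, which is to use the pooled mean without the indicator.
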